3.0 METHODOLOGY

We will conduct a clinic-randomized trial (RCT) to determine the best way to integrate evidence-based depression treatment into non-communicable disease (NCD) clinics in Malawi. We will compare implementation of depression treatment using (1) a basic implementation package vs. (2) an enhanced implementation package.

The basic implementation package will involve identifying an internal coordinator who is one of the full-time on-site providers at the clinic. The internal coordinator provides mentoring to peers and support to leadership in implementing the treatment program and aligning it with clinic priorities.

The enhanced implementation package will combine the internal coordinator with an external quality assurance committee. This committee will complete quarterly audits at the facility to evaluate compliance with the depression treatment protocol as well as providing

high-level support in implementing the treatment program through clinical expertise and limited on-site presence.

Clinics will be randomized 1:1 to receive either the basic or the enhanced implementation package. Clinics will then implement depression treatment as part of standard care at their NCD clinics. All patients at each clinic will receive that clinic's standard care.

To evaluate patient health outcomes, we will enroll a cohort of patients from each NCD clinic. (Sample size and inclusion criteria are below.) Participants will complete assessments at baseline and 6 and 12 months. Assessments will measure sociodemographics, depressive severity, self-reported health, and key medical, structural, and psychosocial factors including trauma history, intimate partner violence, other violence in the home, socioeconomic measures, coping, social support, self-efficacy, experiences of stigma related to mental health, medical and psychiatric comorbidity, and risk factors for hypertension and diabetes. Medical appointment attendance data will be abstracted from clinic records.

We will conduct qualitative interviews to provide context for the primary study findings. In year 3, we will interview a subsample of 8 patients (4 in each arm: 2 with depression remission and 2 who remained depressed) to understand their experiences with each intervention. We will ask about satisfaction with and engagement in each intervention component and barriers and facilitators to retention in care. At 3 higher and 3 lower performing clinics (6 clinics total), we will interview clinic directors (District Medical Officers), Clinical Coordinators, NCD providers, Friendship Bench counselors, and SHARP research assistants (n = 6 clinic directors, 6 Clinical Coordinators, 12 NCD providers, 6 Friendship Bench counselors, and 6 SHARP research assistants) to contextualize implementation strategy and intervention acceptability and fidelity. We will also assess implementation climate and intervention-values fit. Finally, we will interview key MOH representatives (n=3) to understand the facilitators and barriers to future scale up. In year 4, we will interview 3 hospital staff and 1 SHARP research assistant from each of the 10 study sites (n=40). These interviews expand upon the findings of the year 3 qualitative interviews and will add further depth to the study's primary findings.

3.2 Population

Patients at the participating NCD clinics who meet the following eligibility criteria will be invited to participate.

Inclusion criteria

1. Ages 18-65 years (antidepressant treatment considerations differ for those <18 or >65 years, and these age groups are expected to be very rare in the target clinics),
2. Current or new patient receiving care for either hypertension or diabetes from the NCD clinic at a study site listed in Section 3.1, and
3. Elevated depressive symptoms (PHQ-9 score ≥ 5).

Exclusion criteria

Patients will be excluded if they have a history of bipolar or psychotic disorder, or show emergent threat of self-harm.

3.3 Duration

The Phase II RCT will occur during project years 2-4 (November 2018-October 2021). We will complete training for providers and staff in the two arms. We will initiate the two implementation strategies at all clinics and spend 24 months recruiting participants. Follow-up monitoring will extend an additional 12 months, through year 4.

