3.4 Sample Size

A total of 116 patients will be enrolled from each clinic to measure clinical outcomes over time, for a total sample of 1,160 patients recruited over a two-year period.

Sample size and power: Assumptions. Statistical power analyses are based on these assumptions: (1) two-sided statistical significance tests; (2) Type I error $\alpha=0.05$; (3) power ($1-\beta$) of 80%; (4) intraclass correlation coefficient (ICC) of 0.02 for the mental health outcome. For behavioral interventions, clinic-level ICCs normally range from <<0.01 to 0.04. For effect size, up to 30% of depressive episodes may remit without treatment. We assume that the basic implementation package may improve depression treatment, so we assume the incidence of depression remission to be 40% with the basic package. A difference of 15 percentage points or more in depression remission in the enhanced arm relative to the basic arm would be clinically meaningful and worth detecting. Therefore the study is powered to detect this difference. Based on extremely high retention success in prior studies and the short time frame of the primary outcome (3 months), 90% retention is assumed. Given these assumptions, we will enroll 116 participants per clinic from 10 clinics, or 1,160 participants overall. Fewer clinics would require a prohibitive sample size.

We will also complete qualitative interviews with 8 patients, 6 clinic directors, 6 Clinical Coordinators, 12 providers, 6 Friendship Bench counselors, 6 SHARP research assistants, and 3 MOH officials. These interviews will take place in Year 3 of the study. Given standard sample size guidelines for qualitative data collection, this sample size is expected to be sufficient for theme saturation in each group.

We will additionally conduct 16 cognitive interviews and 200 structured surveys with nurses, clinicians and peer friendship bench counsellors to evaluate providers' perceptions of stigma and acceptance towards individuals with mental health disorders. These

interviews and surveys will take place in Year 3 of the study. The desired sample size for cognitive interviewing, while adequate for the inclusion of variety of staff, reflects the expectation that data saturation will be reached with a relatively small number of participants. The desired sample size for structure interview is reflective of the expectation that approximately 10 participants are needed for every survey item in the measure.

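### Patients appear to be recruited after their clinic's arm is set, and no stated rule independent of arm decides who is screened or who fills the 116 places per clinic

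*Combined protocol and SAP*

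**What the plan says.** **Order of events.** Section 3.0: "Clinics will be randomized 1:1 to receive either the basic or the enhanced implementation package", followed by "Clinics will then implement depression treatment as part of standard care at their NCD clinics". Section 3.3 lists three steps in turn: "We will complete training for providers and staff in the two arms", then initiation of the strategies, then recruitment ("We will initiate the two implementation strategies at all clinics and spend 24 months recruiting participants").

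**Who enters.** Section 3.2: "Patients at the participating NCD clinics who meet the following eligibility criteria will be invited to participate". The criteria are the same in both arms and broad: "Current or new patient receiving care for either hypertension or diabetes from the NCD clinic", with "Elevated depressive symptoms (PHQ-9 score ≥ 5" as the symptom threshold. Section 3.4: "A total of 116 patients will be enrolled from each clinic to measure clinical outcomes over time".

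**What is not stated.** The available text does not say who screens, whether that person knows the arm, which attendees are screened, how the 116 are chosen if more qualify, or how they are spread over the 24 months. It describes no screening log and no listing of patients before randomisation.

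**Analysis.** Section 4.0 gives an intention-to-treat GEE comparison with a log link and a bias-corrected robust variance. It names no baseline covariates and no comparison of the enrolled cohorts by arm.

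**The concern.** Randomising clinics makes the clinics comparable in expectation. It makes the enrolled patients comparable only if they enter the cohort in the same way in both arms. If the arm is already in operation when a patient is approached, the choice of whom to screen, whom to invite and who agrees can depend on arm. The inclusion criteria leave room for this, since they admit new and long-standing patients and anyone from mild symptoms upwards, and these groups may well remit at different rates.

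A resulting difference in case mix would appear in H2 (remission) and H3 (hypertension and diabetes control) as an effect of the strategy, or would hide one. A variance correction does not remove bias, and neither does enrolling more patients. H1 concerns provider fidelity taken from clinical records and is not part of this point.

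**Working it through.** **1. The plan's own figure.** Inputs from Section 3.4: 40% vs 55% remission, two-sided 5% test, 80% power, ICC 0.02, 90% retention, 10 clinics (5 per arm).

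- Independent n per arm = (1.960 + 0.842)² × (0.40×0.60 + 0.55×0.45) / 0.15² = 170.06.
- Evaluable per clinic, m, solves 5m = 170.06 × [1 + (m − 1)×0.02]. So m = 170.06×0.98 / (5 − 170.06×0.02) = 104.2.
- Enrolled per clinic = 104.2 / 0.90 = 115.8, rounded up to **116**.

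The sample size reproduces and is not in dispute. Over 24 months it is 116/24 = 4.8 enrolments per clinic per month.

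**2. Precision of the design.** Evaluable per clinic = 116×0.90 = 104.4. Design effect = 1 + 103.4×0.02 = 3.068. Effective n per arm = 5×104.4/3.068 = 170.1. With no true effect and 40% remission in both arms, SE = √(2×0.40×0.60/170.1) = 0.0531.

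**3. Illustrative bias.** The documents give no case-mix figures, so these inputs are assumptions. Bias = (arm difference in the share of milder patients) × (remission in milder patients − remission in others).

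Rejection rate of a nominal 5% test with no true effect (z) = 1 − Φ(1.96 − bias/SE) + Φ(−1.96 − bias/SE). The t version uses the noncentral t on 10 − 2 = 8 df.

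| Remission gap | Shift in mild share | Bias (points) | Error, z | Error, t (8 df) |
|---|---|---|---|---|
| 20 points | 10 points | 2 | 6.6% | 6.3% |
| 20 points | 20 points | 4 | 11.7% | 10.2% |
| 30 points | 10 points | 3 | 8.7% | 7.9% |
| 30 points | 20 points | 6 | 20.4% | 17.0% |

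Example: a 3-point bias gives 0.03/0.0531 = 0.565, so the error is 1 − Φ(1.395) + Φ(−2.525) = 8.7%. Over gaps of 20 to 40 points and shifts of 5 to 30 points, the bias runs from 1 to 12 points and the z error from 5.4% to 61.8%.

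**4. If the bias runs against the enhanced arm.** A true 15-point effect then appears as 15 minus the bias, with basic-arm remission at 40%.

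| Bias | Apparent difference | Power, z | Power, t (8 df) |
|---|---|---|---|
| 0 | 15 points | 80% | 69% |
| 3 points | 12 points | 61% | 50% |
| 6 points | 9 points | 39% | 32% |

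The two columns use different references and should not be mixed.

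**5. H3.** The documents give no control rate or ICC for hypertension or diabetes, so no figure is offered. The mechanism is the same.

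**The case against.** **Timing is inferred.** A reader might conclude that every patient is enrolled with the arm known for certain. The documents do not say so. The order rests on the sequence of sentences in Sections 3.0 and 3.3. Recruitment of 24 months plus 12 of follow-up fills all 36 months of November 2018 to October 2021, leaving no time for training and initiation first. The workplan table shows no timing marks in the copy available, and Section 3.1 was not available and could hold relevant detail. Nothing says what interviewers or patients know about the arm. This removes the absolute claim; the natural reading, that recruitment follows allocation, stands.

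**Discretion is conditional.** Section 3.2 can be read as inviting every eligible patient, and 116 is a sample-size target that is nowhere called a cap. If a clinic needs the full 24 months to find 116, little choice of whom to invite remains. This stands for such clinics, but the documents give no counts of eligible patients, and who is screened is undefined either way.

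**The mechanism is not documented.** A reader might picture audited clinics steering milder or more engaged patients into the cohort. No passage describes clinic staff referring patients. Interviews are done by trained research interviewers (Section 3.5). The audits assess compliance with the treatment protocol, and all patients receive their clinic's standard care whether or not they take part. Selection unrelated to arm would add between-clinic variance, which the robust variance addresses. So only a risk is shown.

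**Adjustment could deal with the illustration.** Depressive severity is measured at baseline, so a bias arising wholly through severity could be removed by stratifying on it. This is correct and is a reason to prespecify adjustment. It does not reach unmeasured traits such as motivation.

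**Conclusion.** The point holds as a gap in the recruitment and analysis plan. As Sections 3.0 and 3.3 read, recruitment follows allocation, and the available text gives no approach rule independent of arm. Where eligible patients exceed those enrolled, arm-related selection or consent could bias H2 and H3, and Section 4.0 has nothing that would detect or reduce it.

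The documents do not show that bias occurred, in which direction, or how large it would be. The H2 error rates of about 8-9% for a 3-point bias and 17-20% for a 6-point bias depend on assumed remission gaps and case-mix shifts, with the plan's ICC of 0.02 and 90% retention. It should be corrected because selection on unmeasured traits cannot be repaired at analysis and a rule at the point of approach is cheap. Confidence is medium, because the timing is inferred.

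**What to change.** **Section 3.2.** State that research interviewers approach NCD attendees consecutively, or from a centrally issued start point in clinic attendance records; give the PHQ-9 to everyone approached; and invite all who qualify until that period's target is met. Keep a log by clinic of patients approached, screened, eligible and consented. The protocol mentions attendance data in clinic records but does not say whether they list attendees in a usable order. If they do not, use the consecutive option.

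**Section 4.0.** Prespecify a comparison of the enrolled cohorts by arm, an H2 analysis adjusted for baseline PHQ-9, and an H3 analysis adjusted for baseline blood pressure or glucose.

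**Limits.** The rule narrows the room for selection but does not conceal allocation: interviewers may still know the arm, and consent may still differ. Adjustment covers only measured differences.

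**If recruitment has closed.** Version 1.9 is dated November 2022, after the window in Section 3.3. In that case the Section 4.0 changes can still be made, and the report can describe how patients were approached, with whatever screening and enrolment counts exist.

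**Cost.** Protocol wording, a short log, a little more screening time, slower filling of the target at some clinics, and a few extra model parameters with only 10 clusters. The sample size does not change.

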3.4 Sample Size

A total of 116 patients will be enrolled from each clinic to measure clinical outcomes over time, for a total sample of 1,160 patients recruited over a two-year period.

Sample size and power: Assumptions. Statistical power analyses are based on these assumptions: (1) two-sided statistical significance tests; (2) Type I error $\alpha=0.05$; (3) power ($1-\beta$) of 80%; (4) intraclass correlation coefficient (ICC) of 0.02 for the mental health outcome. For behavioral interventions, clinic-level ICCs normally range from <<0.01 to 0.04. For effect size, up to 30% of depressive episodes may remit without treatment. We assume that the basic implementation package may improve depression treatment, so we assume the incidence of depression remission to be 40% with the basic package. A difference of 15 percentage points or more in depression remission in the enhanced arm relative to the basic arm would be clinically meaningful and worth detecting. Therefore the study is powered to detect this difference. Based on extremely high retention success in prior studies and the short time frame of the primary outcome (3 months), 90% retention is assumed. Given these assumptions, we will enroll 116 participants per clinic from 10 clinics, or 1,160 participants overall. Fewer clinics would require a prohibitive sample size.

We will also complete qualitative interviews with 8 patients, 6 clinic directors, 6 Clinical Coordinators, 12 providers, 6 Friendship Bench counselors, 6 SHARP research assistants, and 3 MOH officials. These interviews will take place in Year 3 of the study. Given standard sample size guidelines for qualitative data collection, this sample size is expected to be sufficient for theme saturation in each group.

We will additionally conduct 16 cognitive interviews and 200 structured surveys with nurses, clinicians and peer friendship bench counsellors to evaluate providers' perceptions of stigma and acceptance towards individuals with mental health disorders. These

interviews and surveys will take place in Year 3 of the study. The desired sample size for cognitive interviewing, while adequate for the inclusion of variety of staff, reflects the expectation that data saturation will be reached with a relatively small number of participants. The desired sample size for structure interview is reflective of the expectation that approximately 10 participants are needed for every survey item in the measure.

We will also complete Year 4 end point qualitative interviews with a similar group of health workers and SHARP staff interviewed during Year 3. In Year 4, these interviews will take place at each of SHARP's 10 study sites, specifically: 10 clinic directors, 10 Clinical Coordinators, 10 providers, and 10 SHARP research assistants (n=40).

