2.0 HYPOTHESES AND STUDY OBJECTIVES

2.1 Hypotheses

Our primary objective is to compare two different implementation strategies to facilitate ongoing MOH efforts to scale up evidence-based depression treatment within NCD care. Specifically, we hypothesize that:

H1. Compared to providers at clinics receiving the basic implementation package, providers at clinics receiving the enhanced implementation package will deliver depression treatment with greater fidelity.

H2. Compared to patients receiving care at clinics with the basic implementation package, patients receiving care at clinics with the enhanced implementation package will be more likely to achieve depression remission at 6 and 12 months.

H3. Compared to patients receiving care at clinics with the basic implementation package, patients receiving care at clinics with the enhanced implementation package will be more likely to have well controlled hypertension and diabetes at 6 and 12 months.

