2.2 Study Objectives

Phase I (formative studies, not covered in this protocol)

Results from Phase I will inform the implementation of the Phase II research study comparing two different implementation strategies.

- We conducted in-depth interviews with providers, clinic directors, and Ministry of Health representatives to adapt the intervention to the NCD care context in Malawi.
- We conducted site visits to assess key contextual and structural characteristics of each clinic including organizational readiness for change, management support, patient panel size and demographics, number and training level of staff, staff-to-patient ratio, typical daily patient volume, hours of operation, and storage facilities for medications.

Phase II (Randomized Trial)

- Compare providers' fidelity of depression treatment between clinics receiving the basic implementation package vs. clinics receiving the enhanced implementation package.
- Compare patients' depression remission at 6 and 12 months between those receiving care at clinics with the basic implementation package vs. those receiving care at clinics with the enhanced implementation package.
- Compare patients' well controlled hypertension and diabetes at 6 and 12 months between those receiving care at clinics with the basic implementation package vs. those receiving care at clinics with the enhanced implementation package.

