3.5 Data Sources

Data will come from the following sources:

1. Patient participants: The 1,160 patients will complete structured interviews, either in-person or via phone, with trained interviewers at baseline, 3, 6 and 12 months. Research interviewers will also measure blood pressure, blood glucose, height, and weight.
2. Qualitative interviews with patients: Additional information on acceptability of the depression treatment program will be gathered via in-depth interviews with a subset of patients (n=8).
3. Clinical records: Information on depression treatment delivery and fidelity will be abstracted from clinical records.
4. Clinic director, Clinical Coordinator, provider, Friendship Bench counselor, SHARP research assistant, and MOH interviews: Information about implementation strategy and intervention acceptability and fidelity from in-depth interviews with clinic directors (n=6), Clinical Coordinators (n=6), providers (n=12), Friendship Bench counselors (n=6), SHARP research assistants (n=6), and MOH officials (n=3). Cognitive interviews will be conducted with providers (n=8) and Friendship Bench counselors (n=4). Structured surveys will be conducted with providers, friendship bench counselors, and clinic leadership (n=200).
5. End point qualitative interviews at each of SHARP's study sites will focus on additional factors affecting implementation strategy fidelity like organization climate, organizational change, and barriers and facilitators to strategy implementation. Specifically, this information will be gathered from clinic directors (n=10), Clinical Coordinators (n=10), providers (n=10), and SHARP research assistants (n=10).

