4.0 STATISTICAL ANALYSIS PLAN

Analysis of implementation and effectiveness outcomes will be intent-to-treat comparisons between arms. Comparisons will be made using generalized estimating equation models with a log link and binomial error distribution to compare proportions. The design effect introduced by clinic-level randomization will be addressed using the bias-corrected robust variance estimate for GEE models recommended given the small number of clusters. A secondary, as-treated analysis will restrict the analysis to those who received a minimum

dose of the depression treatment program (e.g., at least three depression care management appointments).

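### The primary outcome is placed at 3 months in Section 3.4, but the remission hypothesis and objective name only 6 and 12 months, and the analysis plan names no time point

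*Combined protocol and SAP*

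**What the plan says.** - **Section 3.4 (Sample Size)** is the only place that speaks of a primary outcome with a time attached: "Based on extremely high retention success in prior studies and the short time frame of the primary outcome (3 months), 90% retention is assumed". The only outcome powered there is depression remission, 40% in the basic arm against 55% in the enhanced arm.
- **Section 2.1 (H2)** predicts that patients in the enhanced arm "will be more likely to achieve depression remission at 6 and 12 months". H1 (fidelity), H2 (remission) and H3 (hypertension and diabetes control) all stand under one statement: "Our primary objective is to compare two different implementation strategies".
- **Section 2.2** repeats the time points of H2: "depression remission at 6 and 12 months between those receiving care at clinics".
- **Section 3.0** gives the schedule as "Participants will complete assessments at baseline and 6 and 12 months".
- **Section 3.5** gives it as "with trained interviewers at baseline, 3, 6 and 12 months".
- **Section 4.0** opens with "Analysis of implementation and effectiveness outcomes will be intent-to-treat comparisons between arms". It then gives the model and variance estimator, but no primary outcome, no time point and no rule for several time points.

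**The concern.** Someone who takes the primary outcome from 3.4 would test remission at 3 months. Someone who takes it from H2 would test 6 and 12 months. Under the schedule in 3.0, the 3-month outcome would not even be measured. Section 4.0 does not settle the matter, so the primary comparison could be picked after the results are known.

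Even if H2 governs, it does not say whether remission must differ at both visits or whether one is enough. The first reading costs power. The second raises the false-positive rate above the stated 0.05 unless alpha is divided.

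One of the two grounds for 90% retention, the short time frame, also belongs to a 3-month outcome that no hypothesis names.

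**Working it through.** **Inputs, all from 3.4 and 3.0:** two-sided alpha 0.05, power 80%, ICC 0.02, 40% versus 55% remission, 90% retention, 116 enrolled per clinic, 10 clinics randomized 1:1 (5 per arm).

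**1. Reproducing the plan's figure (one test, unpooled z-test)**

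- Analysed per clinic: m = 116 × 0.90 = 104.4
- Design effect: 1 + (104.4 − 1) × 0.02 = 3.068
- Effective n per arm: 5 × 104.4 / 3.068 = 170.1
- Standard error: √[(0.40×0.60 + 0.55×0.45) / 170.1] = 0.0535
- Standardized difference: 0.15 / 0.0535 = 2.802
- Power: Φ(2.802 − 1.960) = 80.0%

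With 115 per clinic the result is 79.9%, so this formula gives exactly 116. The calculation is sound for one test at one time point.

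**2. Retention at a later visit.** The plan gives no figure for 6 or 12 months, so 80% and 70% are assumptions.

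| Retention | m | Design effect | Effective n per arm | Power |
|---|---|---|---|---|
| 90% | 104.4 | 3.068 | 170.1 | 80.0% |
| 80% | 92.8 | 2.836 | 163.6 | 78.5% |
| 70% | 81.2 | 2.604 | 155.9 | 76.5% |

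The loss is small because clustering, more than the number per clinic, limits precision.

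**3. Two time points, 90% retention.** The calculation is bivariate normal and assumes 40% versus 55% at both visits; 3.4 ties those rates to no visit. The correlation between the two test statistics is also assumed.

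| Rule | Corr. 0.5 | Corr. 0.7 | Corr. 0.9 |
|---|---|---|---|
| Both succeed, 0.05 each | 68.7% | 71.3% | 75.0% |
| At least one succeeds, 0.025 each | 85.3% | 82.0% | 77.4% |

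At 0.025, power for each time point on its own is 71.3%.

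**4. False positives if any one time point counted at 0.05.** At correlation 0 the two-sided bounds are 1 − 0.95² = 9.75% for two time points and 1 − 0.95³ = 14.3% for three. Counting only results in favour of the enhanced arm, they are 1 − 0.975² = 4.9% and 1 − 0.975³ = 7.3%, against 2.5%.

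| Any one of | Direction | Corr. 0 | Corr. 0.5 | Corr. 0.7 | Corr. 0.9 |
|---|---|---|---|---|---|
| 6, 12 months | two-sided | 9.75% | 9.1% | 8.3% | 7.0% |
| 3, 6, 12 months | two-sided | 14.3% | 12.5% | 10.9% | 8.4% |
| 6, 12 months | favouring enhanced | 4.9% | 4.5% | 4.2% | 3.5% |
| 3, 6, 12 months | favouring enhanced | 7.3% | 6.3% | 5.5% | 4.2% |

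If both 6 and 12 months must succeed, the error favouring the enhanced arm is 0.5% at correlation 0.5 and 1.5% at 0.9, below 2.5%.

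**5. Small number of clinics.** Section 4.0 calls for the "bias-corrected robust variance estimate for GEE models recommended given the small number of clusters" but gives no reference distribution. With a t reference on 8 df (10 clinics minus 2, an assumption), power for one test at 0.05 is 69.1%, and at 0.025 it is 54.8%. Winning both time points has power of about 54–62%, and winning at least one at 0.025 each about 73–63% (correlations 0.5–0.9, simulated from clinic means). The fall from 80% to 69% arises whichever time point is chosen, so it is not a result of this contradiction.

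**The case against.** Only 3.4 uses the term primary outcome. Sections 2.1 and 2.2 never call remission at 6 and 12 months the primary outcome, so 3 months could be primary and the later visits secondary. This does not remove the conflict. On that reading no hypothesis or objective states the trial's primary outcome, and the secondary time points stand under the primary objective. It is true that remission as the primary outcome is inferred from the power calculation. The inference is the natural one, since nothing else is powered.

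The inflated error rates describe a decision rule that the plan never states, and correlation 0 is implausible for the same patients in the same clinics. Both points stand, so those figures are conditional bounds. The plan does state two-sided tests at 0.05; what it lacks is a primary outcome, a time point and a multiplicity rule.

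The retention assumption also rests on prior studies, and its effect on power is minor. That stands as well: no increase in sample size has been shown to be needed.

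Part of the front matter and the text between 3.0 and 3.2 were not available for review. Further text could add a statement, but it could not make the sections quoted here agree.

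**Conclusion.** The concern holds, with high confidence, and must be fixed. The current text of 2.1, 2.2 and 3.4 disagrees on when the primary remission comparison is made, 3.0 and 3.5 disagree on whether a 3-month visit exists, and 4.0 does not resolve either conflict. The finding rests on the unfixed primary comparison, not on a proven loss of power or a proven inflation of error.

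The stated 80% power applies to one test at one time point. How far power or error would move under a two-visit reading depends on the decision rule, on the assumed correlations and, for power, on the same 15-point difference holding at both visits.

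**What to change.** Before any analysis by arm, the sponsor should name one primary remission time point and state it identically in 2.1, 2.2, 3.4 and 4.0. The schedule in 3.0 should be made to agree with 3.5. A possible sentence for 4.0:

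> *The primary comparison is depression remission at [time point] months, enhanced versus basic arm, two-sided alpha 0.05; remission at the other time points is secondary; [status of H1 and H3, sponsor's choice].*

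- If both 6 and 12 months are to be primary, say whether both must succeed or either suffices with alpha control, and give the resulting power.
- If the primary time point is not 3 months, correct it in 3.4 and restate the retention basis and power for that visit.
- The latest listed version is dated November 2022, after the trial's planned end in October 2021 (3.3), and the documents do not say whether results by arm had been seen. If they had, say so and report all three time points without calling the choice prespecified.

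**Cost:** wording in five sections (2.1, 2.2, 3.0, 3.4, 4.0) and no new data, because 3.5 already includes all three visits. Results at the other time points can no longer be presented as primary. Making two visits primary also costs power, by the amounts in steps 3 and 5 of the working; the t-based figures there should be read against their own single-test baseline of 69%, not against 80%.
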